Tier 1 trainees must own a smart phone and commit to cascading their training to ≥ 5 tier 2 health workers. Tier 2 health workers must own a feature phone as a minimum. Whatever the existing gender balance of health workers in each health facility, we will require health facilities to nominate the same ratio of trainee places to women health workers.

Patients

Adults ≥ 18 yrs receiving treatment and/or monitoring for at least one of Type 2 diabetes, Hypertension, Chronic Obstructive Pulmonary Disease or Coronary Heart Disease. These conditions are common, patients are vulnerable to poor outcomes from communicable diseases and they require contact with health facilities three times per year.

Exclusion criteria are no access to a mobile phone or fixed phone in their community; those identified by health workers as nearing end of life or currently severely ill, carers consulting on a another person's behalf and those unable to provide informed consent.

Informed Consent

Consent on behalf of each cluster

The country principle investigator (PI) is responsible, with the research team, for approaching health facilities to determine their interest in participating. The country PI will verbally inform them of the

study, share the research protocol and discuss their eligibility. When a facility confirms interest and eligibility, a partnership contract will be developed between the host university and the facility management. This contract will document the responsibilities of each partner and the financial details of the contract. The REaCH trial offers each facility funding for each facility manager and administrator to supply the required data, airtime support for the trainees to deliver remote consultations and for their time to engage in training and cascading. Once the contract is signed the trial can commence.

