- 5) Patient engagement with their health: Patient Activation Measure (PAM-13) aims to understand the knowledge, beliefs and skills required by people to enable them to manage their long-term conditions [13]. It has been successfully used in African populations [14]. Our previous research found that patient activation increases with remote consulting [4]. Also that the PAM-13 [12] has face and content validity for assessing the impact of remote consulting.
- 6) Patient safety is assessed by counting the number of investigations processed by the facility monthly and matching these to the patient’s consultation type. An increase may indicate a higher safety threshold when the person cannot be examined. A decrease may indicate missed health needs. The meaning and impacts of changes in this indicator will be explored in the process evaluation.

Evidence from the secondary outcomes will be explored in the process evaluation.

Sample size

The trials in Nigeria and Tanzania will take place independently, but with identical designs. We plan to recruit 20 clusters in each country for the trial and we expect there to be an average of 100 active eligible patients at any one time in each cluster. We describe each of these active patients in each cluster as an open cohort- patients will leave the cohort if they are not seen for >5 months and newly diagnosed patients meeting the eligibility criteria can join the cohort. The trial has both non-inferiority and superiority inferential goals: we hypothesise the intervention will increase the remote consultation but not affect consultation trust, for example. We therefore opt to determine “minimum detectable effect” sizes rather than power to indicate the precision of the trial and the likely sizes of effect for which we can provide strong evidence of superiority or non-inferiority. Our calculations are based on the statistical models reported below and a power of 80%, a type I error rate of 5%, an ICC of 0.05, and a CAC of 0.8. The assumptions about each outcome and minimum detectable effect sizes are reported in the Table below.

| Outcome | Baseline assumed | Denominator or population | Treatment effect | Lower minimum | Upper minimum |
|----------------|-------------------------|----------------------------------|-------------------------|----------------------|----------------------|

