|----------------|-------------------------|----------------------------------|-------------------------|----------------------|----------------------|

| | | | | detectable effect | detectable effect |
|--|--|-----------------------------|----------------------|--------------------------|--------------------------|
| Face to face consultation/prescription rate | 0.25 consults/prescriptions per person-month | All active patients (n=100) | Incidence rate ratio | 0.84 | 1.20 |
| Remote consultation rate | 0.02 consults per person-month | All active patients (n=100) | Incidence rate ratio | 0.77 | 1.56 |
| Patient trust | 3.5 (sd=0.5) | Sampled patients (n=20) | Absolute effect | -0.07 | 0.07 |

A change in either consultation rate of an equivalent of one visit per person-year is considered “clinically significant”, which is well outside our minimum detectable range. Similarly, we will be able to identify reasonably small changes (~0.15 standard deviations) in patient trustworthiness score, although we do not hypothesise a change in this outcome.

Patient participant recruitment and sampling

At the study commencement each cluster provides the study with a pseudonymised list of active patients, giving us a patient ID and the basic information, we need from each patient (age, sex and eligible diagnosis). At the clinic they will have a link to patient ID with the patient’s record but we will not have access to the patient personal data. This is the open cohort for each cluster.

Each month we collect from each clinic a record of the consultations conducted and prescriptions and investigations ordered by the clinic, all they need to provide is the number of visits by type, prescriptions, investigations and any other information we need linked to a patient ID (e.g. patient 1234 had one remote visit, 2 prescriptions). Any additional patients can join the open cohort if they become eligible during the trial period.

Using the information, the research team can calculate outcomes, remove patients that are no longer active/who default, and sample for participation in the trust and patient activation outcomes and the process evaluation interviews. We will return the list of sampled patient identification number to the clinic for them to contact the potential participant so the research team can commence the informed consent processes.

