University of Ibadan will host an independent Data Monitoring and Ethics Committee (DMEC). The Committee comprises experienced researchers and community stakeholders and an independent statistician. The DMEC will liaise with the study statisticians at Birmingham and Ibadan to review unblinded patient safety data. The DMEC will meet during project months 2, 8 and 16 and report to the chair of the TSC. Interim analyses will be undertaken at trial month 6 specifically to monitor participant safety.

Harms

One unblinded co-investigator in each country will hold responsibility for monitoring prescriptions and investigation rates monthly by consultation type across all cluster data. Differences by consultation type of greater than 40% (i.e. equivalent to one visit per patient year) across each cluster will trigger a consideration of whether there could be a participant safety issue. Any such

difference will be investigated with the facility manager to identify and report any adverse or serious adverse events at an individual participant and/or cluster level. Where such events are revealed, this will be reported to the KCL PI, the country PIs and the chair of the DMEC.

Process evaluation

The process evaluation will a) explore patient and health-worker experience of remote consulting b) its impact on healthcare and c) enablers/impediments of remote consulting. It will be informed by:

1. MRC framework for complex intervention process evaluation [20] to understand how REaCH training impacts on health workers and in turn how remote consulting impacts healthcare experience.
2. TRAIN framework to assess how well the train-the-trainer approach works [9].
3. Consolidated implementation framework [21] to understand what enables/hinders implementation of remote consulting.

Participants and sampling

From all trial clusters we will collate data on the REaCH training: number and roles of tier 1 and tier 2 trainees, their sex, their engagement with each part of the training/cascading, and their text written during the REaCH training.

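### The harm trigger equates 40% with one visit per patient-year, but the protocol's own baseline makes one visit 33%; if applied to single cluster-months it can also fire often by chance

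*Protocol*

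**What the plan says.** Under Harms, one unblinded co-investigator per country is responsible for "monitoring prescriptions and investigation rates monthly by consultation type across all cluster data". The rule follows: "Differences by consultation type of greater than 40% (i.e. equivalent to one visit per patient year) across each cluster will trigger" an inquiry. What it sets off is described as: "trigger a consideration of whether there could be a participant safety issue". Any such difference is then taken up with the facility manager, and adverse events that come to light are reported to the investigators and to the chair of the data monitoring committee.

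Other sections bear on the figure in the bracket:

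- The Sample size table gives a baseline of "0.25 consults/prescriptions per person-month" for face-to-face consultations and prescriptions, and "0.02 consults per person-month" for remote consultations.
- The text below that table uses the same yardstick: "A change in either consultation rate of an equivalent of one visit per person-year is considered" clinically significant.
- The patient eligibility criteria say of the eligible conditions that "they require contact with health facilities three times per year".
- On cluster size, the Sample size section says "we expect there to be an average of 100 active eligible patients at any one time in each cluster".

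The protocol gives no formula for the percentage, reference mode, minimum count or expected investigation rate. It names two units: all cluster data for the monitoring, and each cluster for the trigger.

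**The concern.** The trigger is a decision threshold: it settles when somebody looks for harm. It is stated in two forms that the protocol treats as the same, a percentage and a number of visits per year. If they differ, two people applying the rule in good faith can disagree on whether a given difference calls for an inquiry. The bracket also explains a threshold on prescriptions and investigations by a number of visits, and nothing in the protocol makes those interchangeable.

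The second question is whether the data can carry a 40% rule. A cluster has about 100 patients and few remote consultations at baseline. If the rule is read cluster by cluster and month by month, a gap above 40% may be little more than the coarseness of very small counts. Such alarms use up the attention of the one person who has to sort them from real signals.

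**Working it through.** **Step 1. Trying to reproduce the 40%.** Relative difference = 1 visit per year ÷ (monthly baseline × 12).

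- Face-to-face or prescription baseline: 0.25 × 12 = 3.0 per year, in line with the three contacts per year in the eligibility criteria. 1 ÷ 3.0 = 33.3%.
- Face-to-face plus remote: (0.25 + 0.02) × 12 = 3.24 per year. 1 ÷ 3.24 = 30.9%.
- Remote only: 0.02 × 12 = 0.24 per year. 1 ÷ 0.24 = 417%.
- In reverse: 0.40 × 3.0 = 1.2 visits per year. For 40% to be one visit, the baseline would have to be 1 ÷ 0.40 = 2.5 per year (0.208 per month), which the protocol does not state.
- Less usual scales: a fall from 3 to 2 is 1 ÷ 2.5 = 40.0% of the midpoint, or ln(3/2) = 0.405. A rise from 3 to 4 is 1 ÷ 3.5 = 28.6%, or ln(4/3) = 0.288. Neither scale gives 40% in both directions.

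**Step 2. Counts behind one cluster-month.** 100 × 0.25 = 25 face-to-face consultations, 100 × 0.02 = 2 remote consultations, and 100 × 0.25 = 25 prescriptions. Prescriptions per consultation: 25 ÷ 27 = 0.926, about 0.93.

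**Step 3. Why small counts matter.** Take exactly 2 remote consultations against a face-to-face rate of 0.926. The rule fires if the remote rate is below 0.6 × 0.926 = 0.556 or above 1.4 × 0.926 = 1.296. The remote rate can only be 0, 0.5, 1, 1.5 and so on, so only exactly two prescriptions avoid the trigger.

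- At most one prescription per visit: 1 − 0.926² = 14%.
- Poisson count with mean 1.852: 1 − e^(−1.852) × 1.852² ÷ 2 = 73%.

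**Step 4. Letting all counts vary.** I simulated 400,000 cluster-months per scenario with no true difference between modes. Consultations were Poisson with a total mean of 27, and the trigger was |remote − face-to-face| ÷ face-to-face > 0.40. Shares are of cluster-months in which the comparison can be made. At 2 expected remote consultations about 14% usually cannot be evaluated, almost all because no remote consultation took place (e^(−2) = 0.135).

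| Event per consultation | 25 face-to-face, 2 remote | 22 and 5 | 13.5 and 13.5 |
|---|---|---|---|
| Prescriptions 0.93, at most one per visit | 7% | 2.5% | 0.6% |
| Prescriptions 0.93, Poisson | 60% | 46% | 33% |
| Investigations 0.5 (assumed) | 66% | 46% | 31% |
| Investigations 0.3 (assumed) | 83% | 63% | 50% |
| Investigations 0.1 (assumed) | 99% | 90% | 68% |

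Investigations are taken as at most one per visit. In numbers of clusters at baseline uptake, the Poisson case gives 20 × 0.864 × 0.597 ≈ 10 false triggers per month per country, and the at-most-one case 20 × 0.865 × 0.073 ≈ 1.3.

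**Step 5. Larger units, same 40% rule, baseline uptake.**

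| Event per consultation | 20 clusters, one month (500 and 40) | One cluster, 12 months (300 and 24) |
|---|---|---|
| Prescriptions 0.93, Poisson | 2.2% | 7.6% |
| Investigations 0.3 (assumed) | 12% | 23% |
| Investigations 0.1 (assumed) | 43% | 55% |

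Lowering the threshold to 33% does not cure the small counts: the 60% in the Poisson baseline case becomes 65%.

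**The case against.** The strongest reply has five parts.

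- **The consequence is mild.** The trigger opens a consideration and a conversation with the facility manager; it stops nothing. That is true and limits the weight of the point. It does not make the two figures agree.
- **A 40% reading exists.** A fall from 3 to 2 is 40% on a midpoint scale and 0.405 on a log scale. But the protocol names neither scale, and both fail for a rise, which the Secondary outcomes section also treats as informative for investigations.
- **The chance figure depends on the model.** This stands. Between 7% and 60% the difference is only whether a visit can yield more than one prescription. The protocol's own data example, one remote visit with two prescriptions, shows that it can, but not how often. Training is also meant to raise remote uptake, which lowers the share. A reader might infer that the trigger fires mostly on chance. That would need the frequency of true differences, which the protocol does not give.
- **The cluster-month is one reading.** Also right. The monthly wording is attached to monitoring of all cluster data; the trigger sentence names each cluster without a time window. Pooled over clusters, the Poisson figure is 2.2%. That the text permits both readings is part of what needs fixing.
- **The by-type comparison is deliberate.** The Secondary outcomes section matches investigations to consultation type because a remote patient cannot be examined. A reader might want to replace it by trained against untrained months. In a stepped wedge that contrast is confounded with calendar time, and it would give an unblinded co-investigator a running estimate of prescribing, a primary outcome. The protocol does not support that replacement.

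**Conclusion.** On the ordinary reading the stated equivalence is wrong: at the protocol's baseline one visit per patient-year is 33%, and 40% is 1.2 visits. This rests only on the protocol's own figures. The bracket also applies a visit-rate yardstick to prescription and investigation rates without justification.

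The chance-firing part is conditional. If the rule is applied to each cluster each month at baseline uptake, false triggers occur in about 7% to 60% of evaluable cluster-months for prescriptions, depending on whether counts are at most one per visit or Poisson. For investigations the share is 66% to 99% at assumed rates of 0.5 down to 0.1 per consultation. All of these fall as remote uptake rises.

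Two further inferences are not supported. A reader might conclude that the protocol calls prescribing differences of 33% to 40% clinically significant; the Sample size sentence concerns consultation rates only. A reader might also take this trigger for the main safeguard. The Data monitoring section provides for committee review of unblinded safety data and an interim safety analysis at trial month 6, and the steering committee receives risk assessments.

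The point is worth correcting before the rule is used. It does not touch the effect estimates.

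**What to change.** - Reconcile the 40% in Harms with the one-visit figure there and in Sample size. The investigators decide which stands. State which rate it refers to, since the trigger is on prescriptions and investigations and not on visits.
- State the percentage formula and the reference mode.
- Settle the unit: apply the by-type trigger to cumulative data within each cluster and to data pooled across clusters, in place of the two present wordings.
- Show each difference with an interval, so that a gap resting on few remote consultations or rare investigations is seen as such. Larger units alone do not remove this: at an assumed 0.1 investigations per consultation, the pooled month still exceeds 40% by chance in 43% of cases.

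The cost is one paragraph of the protocol, and the data are already collected monthly. The downside is that cumulative data react somewhat more slowly to a sudden change in one cluster.

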In each local trial delivery team, one investigator and 1 research assistant will remain blinded to the month during which REaCH training was delivered to each cluster. Each facility is given a unique identification number consisting of 4 digits. We use four digits to make it more difficult for the research team to recall cluster IDs when discussing with the unblinded education team. This will reduce bias when monthly data collection is undertaken. When education and research teams meet together, clusters will be referred to by identification number only. At the beginning of every data collection activity the researcher will remind the health worker or patient participant not to reveal whether the facility has undertaken REaCH training. Data entry will be undertaken by a database assistant who will be blinded to whether the data is from a cluster in the intervention or the control. At the bi-weekly trial team meetings we will have an agenda item to check with every blinded member whether they think they have been unblinded in relation the identity of a randomised cluster during the previous two weeks. All UK investigators will be blind to cluster randomisation except the Birmingham trial statistician.

Methods: Data collection, management, and analysis

Trial data collection methods

At trial set up each cluster will provide the research team with a pseudonymised whole facility population of eligible patients. This is the open cohort. On the same day/date of every month the clinic will provide the research team with four lists:

- 1) A list of pseudonymised patients who had face to face consultations since the last data period
- 2) A list of pseudonymised patients who had remote consultations since the last data period
- 3) A list of pseudonymised patients who had prescriptions ordered and collected since the last data period
- 4) A list of pseudonymised patients who had investigations ordered since the last data period

From the combined monthly lists of 1 and 2, the research team will generate a random order list of 30 pseudonymised patients to sample for completion of the patient reported outcome data. Once informed consent procedures are completed, the researcher will undertake a structured interview with the participant by telephone to complete the two questionnaires.

Table 1: Complete listing of the trial data collected

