In all trial clusters we will survey facility managers and tier 1 trainees on implementation one month after completion of the REaCH training for the cluster. The timing allows them time to have reflected on the training and start planning delivery. The questionnaire provides the participant opportunity to reflect on implementation. We will collect information on how facilities distributed the airtime allowance across tier 1 and tier 2 trainees.

Observation, interview and prescription data will be collected in each country, from a random sample of five facilities (clusters) who receive the intervention during the first 6 months of the trial, to allow time for implementation prior to data collection.

Consent to process evaluation data collection will be taken along with consent to trial participation.

Training data (all clusters)

Prior to each REaCH training the facilitator will confirm consent to the use of aggregate data about the trainees/training and to the use of trainees' text for analysis in the study process evaluation clarifying that all personal identifiers will be removed before it is shared with the research team. This will be repeated at the end of the training. Trainees will be able to confidentially inform the facilitator if they do not wish their text to be included.

Survey of facility manager and trainees (all clusters)

All tier 1 trainees and the facility manager in all clusters will be invited to complete a questionnaire about implementation of remote consulting.

Observation (2x5 clusters)

We will observe two tier 1 and two tier 2 training sessions. Each REaCH facilitator will provide us with their timetable for training delivery. We will take a stratified random sample of planned training sessions to ensure observation of the range of modules within the training. Where individuals scheduled to attend observed training sessions have not given consent to be observed we will discuss with them their options. They may choose to attend but remain silent or they may choose not to attend. They will be offered a briefing session with the facilitator after the session so they are able to catch up on learning.

Semi-structured telephone interviews (2x5 clusters)

We will interview 3-4 months after training

- the facility manager
- the REaCH facilitator
- two tier 1 and two tier 2 health workers
- four patient trial participants

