Within each cluster and each tier, from among health workers/patients consenting to participate in interviews will take a random sample.

Prescription data (2x5 clusters)

Prior to training and three months after training is complete, we will ask the facility managers to provide us with the timetable of sessions/clinics run at the facility including remote consulting, and identify those where prescriptions may be issued (e.g. we will exclude child immunisation sessions). We will stratify sessions/clinics by mostly remote consulting/mostly face to face and take a random sample of four sessions with a 1-2-week timeframe at each time point (prior to training and three months after training). We will collect prescription data on consecutive patients from each session.

Survey of facility manager and trainees

All tier 1 trainees and the facility manager in each cluster will be invited to complete three brief questionnaires 1) The four item Intervention Acceptability Measure (AIM), the four item Intervention Appropriateness Measure (IAM) and the four item Feasibility of Intervention Measure (FIM)[22]. We will aim to obtain a minimum of two completed questionnaires from each cluster. The REaCH facilitator will ask the tier 1 trainees for permission to give their name and phone number to the research team. Once informed consent is completed the researcher will ask the trainee to complete the four questions by paper, telephone or via email.

Data collection

All data will be collected via the internet or phone or using social distancing at primary care facilities. Appendix 4 contains a participant distress protocol for anyone feeling uncomfortable during an interview.

Training data

Data on number and roles of trainees and engagement with each part of the training/cascading will be collated by facilitators and passed to the research team as aggregate data. Facilitators will extract student text and remove identifiers before passing it to the research team.

Survey of facility managers and Tier 1 trainees

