We will explore the experience of REaCH training, support and cascade and of undertaking remote consulting, how they have deployed remote healthcare themselves and within the facility, what impact this has on their working patterns, facility organisation and the experience of patients, what is working or not and why, and changes needed or made to enable remote consulting (e.g. facility expenditure on airtime, phones, appointment system, guidelines, policy). We will use initial analysis of survey data to inform how we probe during interviews.

REaCH facilitators

We will explore the experience of REaCH training, support and cascade, their understanding of how their trainees planned to or have deployed remote healthcare, what worked well or not in the training and adaptations they made to the training in response to the need of their trainees. We will ask them what enables the Tier 1 trainees to cascade training successfully and what hinders this, and how this cascade fits within other team activities.

Patient trial participants

We will explore their experience of remote consulting and its impact on their healthcare including what is working or not and why, expenditure on airtime and changes needed or made to enable remote consulting.

Prescription data

We will work with each of the clinics on how we collect this to avoid disrupting the clinic and ensuring patient confidentiality. We aim to collect the drug details from each prescription issued in the sampled sessions. We expect this will involve taking a photograph, ensuring the patient's name is not included in the photograph. There may be a step where a carbon copy is made when the prescription is issued which is then photographed.

Analysis

Training data

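### The random draw of four patient interviewees per cluster takes no account of consultation mode, so it does not ensure that interviewees have consulted remotely

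*Protocol*

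**What the plan says.** The Process evaluation section puts this aim first: "The process evaluation will a) explore patient and health-worker experience of remote consulting". For the patient interviews, the Interviews section under Data collection adds: "We will explore their experience of remote consulting and its impact on their healthcare including what is working or not and why". It also lists airtime spending and changes needed to make remote consulting work.

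Interviews take place in each country in facilities chosen as follows: "from a random sample of five facilities (clusters) who receive the intervention during the first 6 months of the trial". On timing, the protocol says "We will interview 3-4 months after training". Each cluster contributes "four patient trial participants", which gives 5 × 4 = 20 per country and 40 overall.

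The selection rule is "Within each cluster and each tier, from among health workers/patients consenting to participate in interviews will take a random sample". Tier applies to health workers, so for patients the only stratum is the cluster. The patients available are those who took part in the survey, who are found as follows (Trial data collection methods): "From the combined monthly lists of 1 and 2, the research team will generate a random order list of 30 pseudonymised patients". List 1 holds face-to-face consultations and list 2 remote ones.

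Two other passages touch interview sampling. Participant timeline in the trial mentions a sampling framework without giving its content. Sex-based equality provides for over-sampling by sex. Neither refers to consultation mode.

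**The concern.** An interview about the experience of remote consulting needs interviewees who have had one. Nothing in the selection rule secures that. If remote consulting rises only modestly after training, a random draw from users of both modes will consist mostly of patients seen face to face. That is also the situation in which the trial most needs to learn why.

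The protocol leans on this component. Under Outcomes, the meaning of changes in prescribing and investigations is left to the process evaluation, and conclusions are to rest on qualitative and quantitative evidence together. Privacy and confidentiality relies on it to learn how private remote calls are in practice for both parties. Policy relevant outcomes promises evidence on how citizens experience remote care compared with face-to-face care, which needs patients from both modes.

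The protocol already uses the missing device elsewhere. Sessions sampled for prescription data are stratified into mostly remote and mostly face to face, and observed training sessions are stratified to cover the range of modules. The patient interviews have no equivalent.

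**Working it through.** The protocol gives no expected number of remote users among interviewees, so there is no figure to reproduce. The check asks what the stated rule yields at the protocol's own rates.

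**Inputs.**
- Baseline face-to-face rate f = 0.25 per person-month (Sample size table: "0.25 consults/prescriptions per person-month").
- Baseline remote rate r = 0.02 per person-month (same table).
- Upper minimum detectable rate ratio for remote consulting: 1.56 (same table).
- Change called clinically significant: one visit per person-year, 1/12 = 0.083 per person-month (text below the table).
- 4 interviewees per cluster and 20 per country.

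The post-training remote rate is not given, so a range is shown.

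**Formulas.** Assume independent Poisson visits, and willingness to be interviewed unrelated to mode. A patient enters the list with at least one visit of either kind in the month (the index month). The chance that such a patient had a remote visit in that month is

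p = (1 − e^(−r)) / (1 − e^(−(f+r))).

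The expected number per country is 20p. The chance that a cluster has none among its four is (1 − p)^4.

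For the baseline rates: p = (1 − e^(−0.02)) / (1 − e^(−0.27)) = 0.0198/0.2366 = 0.084. Then 20p = 1.7, and (1 − p)^4 = 0.705.

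| Scenario | f | r | p | Expected of 20 | None among 4 |
|---|---|---|---|---|---|
| Baseline rates | 0.25 | 0.02 | 0.084 | 1.7 | 0.705 |
| Rate ratio 1.56 | 0.25 | 0.0312 | 0.125 | 2.5 | 0.585 |
| One remote visit per year added | 0.25 | 0.1033 | 0.330 | 6.6 | 0.202 |
| One visit per year moved to remote | 0.1667 | 0.1033 | 0.415 | 8.3 | 0.117 |

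Appendix 5 prints 1.38, not 1.56, for the same original design. That ratio gives p = 0.112 and 2.2 of 20, so the choice between them does not matter here.

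**Longer recall.** An interviewee may also describe a remote consultation from another month since training. Over a window of m months, the chance of any remote visit is p + (1 − p)(1 − e^(−r(m−1))). For m = 3 to 4, the expected numbers of 20 are:
- baseline: 2.4 to 2.7
- rate ratio 1.56: 3.6 to 4.1
- one visit per year added: 9.1 to 10.2
- one visit per year moved: 10.5 to 11.4

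**Risk of a country with none.** (1 − p)^20 is 0.17 at baseline, 0.07 at a rate ratio of 1.56, and below 0.001 when one visit per year is added.

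**The case against.** A reader might infer that almost none of the interviewees will have consulted remotely, and that the process evaluation therefore cannot explore patients' experience of it. The documents do not support that.

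- **Timing.** Interviews are held only in trained facilities, some months after training, and those facilities were chosen to allow time for implementation. The 0.02 rate describes usual care and is a floor. The ratio of 1.56 is a detectable effect, not an expected one. At the change the protocol calls clinically significant, a third or more of interviewees would have had a remote consultation in the index month, and about half over 3-4 months.
- **The protocol's own projections are higher.** Training and capacity building illustrates 400 workers with five remote consultations a day each: 2,000 a day, or 50 per cluster over 40 clusters. This covers all patients, not the eligible cohort, so it is not an estimate of r, but it points upwards.
- **Non-users have something to report.** The evaluation also covers enablers and impediments. Patients in a trained facility who were not offered remote care, could not use it or declined it inform that aim.
- **Other sources exist.** Health workers, managers and facilitators are interviewed too, and the prescription data are stratified by mode.
- **The rule is not described as a simple random sample**, and the sampling framework's content is not shown.

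All of this limits the claim, but the gap remains. The one rule stated does not mention mode. The number of remote users interviewed depends on the size of the effect under test, and no step protects it when uptake is modest. Staff interviews cannot replace patients' own accounts of remote care.

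**Conclusion.** The point holds as a weakness in a stated sampling rule. It does not show that the process evaluation must fail. Selection does not ensure that interviewees have consulted remotely. At modest uptake (baseline rates up to a ratio of 1.56), about 2 of 20 per country would have done so in the index month, or roughly 2 to 4 over 3-4 months. At the same rates, between 58% and 71% of clusters would have no index-month remote user among their four. With one visit per person-year added or moved, the numbers are 6.6 to 8.3 in the index month and about 9 to 11 over 3-4 months, and the problem largely disappears.

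These figures rest on independent Poisson visits, consent unrelated to mode, and a post-training remote rate that the protocol does not give. Clustering of remote use in a few patients or facilities would change them.

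**What to change.** In the interview sampling text (Semi-structured telephone interviews and the selection sentence that follows), stratify the random draw of patients within each cluster by consultation mode. For example, draw two patients with at least one remote consultation since training and two seen face to face only. Where a cluster has fewer than two consenting remote users, take all of them, fill from the other stratum and report how often this happened.

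The fallback will be needed if uptake is low. With 100 active patients, the expected number with a remote visit in a month is 100 × (1 − e^(−0.02)) = 2.0 at baseline and 100 × (1 − e^(−0.0312)) = 3.1 at a ratio of 1.56. Both are before the 60-80% response rate and before consent to interview. The quota therefore gives up to 10 of 20 per country, not a guaranteed 10.

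The cost is a sentence or two of text. The number of interviews is unchanged, and mode is already reported each month by patient ID. The small downside is that interviewees no longer mirror the mode mix of the surveyed patients, which a qualitative sample does not require.
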